#### 9.1.2. Clinical outcome and health resource utilization

Clinical outcomes and health resource utilization are documented using preformed questionnaires and by means of the medical records. Thus, participants will be asked to fill out three questionnaires daily: i) The modified Brief Pain Inventory short form, ii) Bristol Stool Form Scale and iii) Gastrointestinal Symptom Rating Scale (GSRS). For a detailed description of these, see below. From the patients' medical records, the following will be registered: i) presence of local and systemic complications as well as organ failure (transient or persistent), used to classify the severity of AP according to the revised Atlanta criteria (20), ii) need for intensive care unit admission, iii) need for analgesics, iv) nutritional support, v) invasive treatment, vi) duration of hospitalization, and vii) mortality. Total duration of hospitalization, readmission rates and mortality will be determined retrospectively 30 and 90 days after admission using the patients' medical records.

### 9.1.3. Questionnaires

#### 9.1.3.1. *The modified Brief Pain Inventory short form*

The modified Brief Pain Inventory short form is used to subjectively document patients' pain intensity at a visual analogue scale from 0-10 as well as relief from medication and impact on daily functions (interference score) (26).

#### 9.1.3.2. *Bristol Stool Form Scale*

The Bristol Stool Form Scale is an objective assessment of parameters such as stool frequency as well as stool consistency and is used to assess intestinal function (27).

#### 9.1.3.3. *Gastrointestinal Symptom Rating Scale*

The Gastrointestinal Symptom Rating Scale (GSRS) is a disease-specific instrument of 15 items combined into five symptom clusters depicting reflux, abdominal pain, indigestion, diarrhea and constipation. The GSRS has a seven-point graded Likert-type scale, where 1 represents absence of troublesome symptoms and 7 represents very troublesome symptoms. The reliability and validity of the GSRS are well-documented, and normal values for a general population are available (28).

### 9.1.4. Biochemistry

Patients with AP will have daily blood samples drawn with the purpose of measuring the systemic inflammatory response (including CRP, IL-6, IL-8, IL-18, TNF- $\alpha$  and CD163). Blood samples (31 ml blood per timepoint) will be drawn at baseline and daily at fixed time points for five consecutive days and two weeks after study termination. Blood samples will be separated by centrifugation and processed as plasma, serum, buffy coat and full blood and subsequently transferred in aliquots to vials labeled with the protocol number (PAMORA\_2020), subject number, and date of sample collection. Samples will be frozen and stored at approximately -80°C or cooler in a freezer at the respective inclusion sites until analysis. The samples will be batch analyzed at a central laboratory to measure the analytes of interest. During the entire study period, a total of 186 ml of blood will be drawn from each AP participant.

After the analyses, all blood samples from both groups of patients will be kept in a biobank for future research purposes and destroyed at the latest 15 years after termination of the study. Ethics according to "databeskyttelsesforordningen" and "databeskyttelsesloven" will be ensured in this regard.

### 9.1.5. Imaging

Patients with AP will have an abdominal contrast enhanced CT scan performed at baseline and after 5 days (+/- 1 day) of treatment. Morphological changes related to AP will be evaluated and described according to the terminology and definitions of the revised Atlanta criteria and the modified CT severity index (20,29).

Furthermore, as an integrated part of the CT exam at day 5 (+/- 1 day) patients will undergo assessment of the intestinal transit time using radiopaque markers given orally on day 3 prior to the CT exam.

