### 7.4.2. Secondary endpoints

- Difference in daily **PASS scores** between subgroups
- Difference in daily assessments of circulating **pro- and anti-inflammatory markers** (including CRP, IL-6, IL-8, IL-18, TNF- $\alpha$  and CD163) as well as **intestinal barrier markers** between subgroups
- Difference in **intestinal permeability** between subgroups measured from 48 to 72 hours after randomization using the oral polyethylene glycol 400/4000 test
- Difference in **intestinal motility** assessed by means of gut/colon transit using a CT-based radiopaque marker method on day 5 (+/- 1 day) between subgroups
- Difference in **pancreatic complications** (e.g. edema, fluid collections and necrosis) assessed and quantified with contrast-enhanced CT on day 5 (+/- 1 day) after randomization (20)
- Difference between subgroups in the following **clinical outcome parameters**: pain intensity and gut function (assessed by questionnaires), quantification of analgesics (separated into opioids and non-opioids), need for nutritional support, disease severity, invasive treatments, intensive care and hospital stay, as well as mortality during total hospitalization
- Difference in **health resource utilization** during hospitalization between subgroups

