## 7.5. Participant timeline

### 7.5.1. Study days

A detailed description of the study procedures is illustrated in Table 1. Patients will be evaluated daily during admission by medical personnel and treated in agreement with the IAP/APA evidence-based guidelines for the management of AP (2). As part of the study, they will receive daily infusions with methylnaltrexone or matching placebo, and have the following examinations performed: i) clinical outcome and patient symptoms will be evaluated by means of both well-validated questionnaires and information from the patient's medical records (see section 9.1.2.), ii) the PASS score will be obtained daily and used to document the primary endpoint 48 hours after randomization, iii) blood samples (including C-Reactive Protein (CRP), interleukin (IL)-6, IL-8, IL-18, tumor necrosis factor alpha (TNF- $\alpha$ ) and cluster of differentiation 163 (CD163)) will be drawn

daily with the purpose of evaluating the systemic inflammatory response, and iv) an abdominal contrast-enhanced CT study will be performed at inclusion and after conclusion of treatment at day 5 (+/- 1 day) to document the presence and extent of pancreatic inflammation, fluid collections and necrosis according to the definitions given in the revised Atlanta criteria (20). As an integrated part of the CT exam at day 5 (+/- 1 day) patients will undergo assessment of the colon/gut transit time using radiopaque markers given orally in the morning on day 3 up to the planned CT exam. Finally, the intestinal permeability will be evaluated by a polyethylene glycol (PEG) 400/4000 test (see section 9.1.5.) 48 hours after randomization. At hospital discharge, patients are invited for a follow-up visit on day 14 (+/- 2 days) after randomization where the outcomes assessed during hospital admission (blood test and questionnaires including the PASS score) will be reassessed. Patients ready for discharge prior to completing five days treatment with methylnaltrexone will be handled according to the following:

- < 48 h of treatment: All data collection will be terminated upon discontinuation of the study medication and participant is regarded as dropout.

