- ≥ 48 h of treatment, but discharge before day 5: Participant will be lost to follow-up on the following outcomes: daily PASS scores, blood samples, vital signs, quantification of need for analgesics, nutritional support, intravenous fluid resuscitation and antibiotics, and data will be analyzed using the Last-Observation-Carried-Forward method (see section 9.3.). The participant will be asked to complete questionnaires at home and they will be offered a follow-up CT scan in an outpatient setting on day 5 (+/- 1 day). Furthermore, they will be invited to participate in the 14-day follow-up and readmission rates as well as mortality will be registered retrospectively.

Randomization	Methylnaltrexone or placebo (0.15 mg/kg/day)				End of study	Follow-up
Baseline	24±2 hours	48±2 hours	72±2 hours	96±2 hours	120±2 hours	14±2 days
PASS	PASS	PASS	PASS	PASS	PASS	PASS
Clinical outcome	Clinical outcome	Clinical outcome	Clinical outcome	Clinical outcome	Clinical outcome	Clinical outcome
Blood samples	Blood samples	Blood samples	Blood samples	Blood samples	Blood samples	Blood samples
		Intestinal permeability		Intestinal transit time		

Computed tomography				Computed tomography	Health resource utilization
---------------------	--	--	--	---------------------	-----------------------------

**Table 1:** Participant timeline. PASS; pancreatitis activity scoring system.

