2.3. Exploratory Objectives

The exploratory objectives are to examine the effects of methylnaltrexone treatment on the immune system, the gastrointestinal tract, and the pancreas. This is to examine whether treatment with methylnaltrexone may reverse potentially opioid-induced changes to these organs.

The exploratory outcomes are listed below:

- Difference between treatment groups on daily levels of circulating pro- and anti-inflammatory blood markers during treatment and at 14-day follow-up
- Difference between treatment groups in intestinal permeability measured based on the polyethylene glycol (PEG) 400/4000 test (16). Following ingestion of a PEG solution containing 5 g PEG 400 and 5 g PEG 4000 dissolved in 100 ml water, patients will have their urine collected for 24 hours. The small size molecules (PEG 400) traverse the intestinal barrier freely, independent of barrier function loss, whereas the large size molecules (PEG 4000) only cross the intestinal wall and becomes detectable in urine in

case of intestinal barrier function loss. Based on the ratio between the two molecules measured in the urine, we can approximate the intestinal permeability

- Difference between treatment groups on gut transit time assessed using a CT-based radiopaque marker method, where the patients are asked to ingest a capsule containing radiopaque markers 48 hours prior to a CT scan. Based on the location of the markers on the CT-scan, the transit time can be approximated
- Difference between groups on the prevalence of pancreatic complications assessed and quantified using a CT-scan according to the Atlanta criteria (10)

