- Pre-existing renal insufficiency (defined as habitual estimated glomerular filtration rate (eGFR) below 45 ml/min/1,73m²)
- End-stage renal impairment requiring dialysis prior to inclusion
- Severe pre-existing comorbidities (assessed by investigator upon inclusion)
- Severe non-pancreaticobiliary infections or sepsis caused by non-pancreaticobiliary disease
- Child-Pugh class B or C liver cirrhosis
- Lactating

5. Data handling

Outcome	Source	Data collection rate	Datatype
PASS-score	From the patients' medical records (vital signs, lab results, quantification of need for opioid treatment), self-reported pain intensity and self-reported tolerance to solid foods	Daily during treatment and at 14-day follow-up	Ratio
Disease severity	Stratified as mild/moderate/severe using information about complications and organ failure from medical files	At 14-day follow-up	Ordinal
Subjective measures of pain intensity	Questionnaire: Pain intensity (current + worst/least pain the past 24 hours using NRS), pain interference score (7 parameters, scores 0-10)	Daily during treatment and at 14-day follow-up	Ordinal
Length of admission	Medical records, no. of days	90 days after randomization	Ratio
Mortality	Medical records; deceased y/n	90 days after randomization	Nominal
Circulating levels of pro- and anti-inflammatory cytokines,	Blood samples	Daily during treatment and at 14-day follow-up	Ratio
Intestinal permeability, gut transit time	Urine samples, CT-scans	Once during treatment (day 2-3)	Ratio
Prevalence of pancreatic complications	Stratified according to the revised Atlanta criteria (21) based on CT-scan	On day 5	Ordinal

Table 1

Delegated trial personnel at each trial center will register the collected data in the electronic case report form (eCRF) using the electronic data capture tool REDCap (Research Electronic Data Capture, version 10.6.26) hosted by the organization of The North Denmark Region. REDCap is a secure browser-based software, which meets all regulatory safety requirements (22,23). Data recording will begin when a participant is included and will occur gradually to the end of the trial. A detailed record of any corrections will be kept within REDCap. REDCap also contains features to improve data validation in the form of predefined variable ranges, options to detect that dates are in correct order and warnings if the forms are not sufficiently filled in.

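### Transit markers are fixed to day 3 but the CT that reads them may fall on day 4, 5 or 6, so the SAP's 48-hour interval is met only for a day 5 CT

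*Protocol*

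**What the plan says.** **Marker timing in the protocol.** Section 9.1.5 describes "intestinal transit time using radiopaque markers given orally on day 3 prior to the CT exam". Section 7.5.1 adds the time of day: "radiopaque markers given orally in the morning on day 3 up to the planned CT exam".

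**CT timing in the protocol.** Section 7.4.2 lists motility as a secondary endpoint, assessed by a "CT-based radiopaque marker method on day 5 (+/- 1 day) between subgroups". Section 9.1.5 has a "contrast enhanced CT scan performed at baseline and after 5 days (+/- 1 day) of treatment". Under Section 7.5.1, patients discharged after at least 48 hours of treatment but before day 5 are "offered a follow-up CT scan in an outpatient setting on day 5 (+/- 1 day". No passage says what happens to the marker day if the CT moves within its window.

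**The SAP.** Section 2.3 counts back from the scan: "patients are asked to ingest a capsule containing radiopaque markers 48 hours prior to a CT scan". It says that transit time is approximated from where the markers lie on the CT, and it lists the outcome as exploratory. Table 1 in Section 5 puts intestinal permeability and gut transit in one row, with urine and CT as sources and one collection time, "Once during treatment (day 2-3". Section 6.2 compares transit between arms with an unpaired t-test or a Mann-Whitney test. Neither uses the time from capsule to CT.

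**The concern.** The protocol ties the capsule to a calendar day and lets the CT float. The SAP ties the capsule to the CT. SAP Table 1 gives a third timing that fits neither. A site that follows the protocol and a site that follows the SAP would do different things whenever a CT is not on day 5.

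This matters because the result is a position at one moment. In the same patient, markers may lie further along at 72 hours than at 24 hours. A location therefore cannot be turned into a transit time without the interval, and two patients with different intervals are not on the same scale. The result is extra variability in a comparison of at most 45 patients per arm. Gut motility is also part of the rationale for the drug in Protocol Section 6.1 and the SAP background.

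**Working it through.** Inputs: markers on day 3 (Protocol 7.5.1 and 9.1.5); CT on day 5 plus or minus one day, so day 4, 5 or 6 (Protocol 7.4.2, 7.5.1 and 9.1.5); intended interval 48 h (SAP 2.3).

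**1. Reproduce the SAP figure.** Interval = (CT day − marker day) × 24 h. At the centre of the window, (5 − 3) × 24 = 48 h. The planned schedule and the SAP agree.

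**2. Apply the same formula across the permitted window.**

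| CT day | Interval with markers on day 3 | Ratio to 48 h | Marker day needed for 48 h |
|---|---|---|---|
| 4 | (4 − 3) × 24 = 24 h | 0.5 | 4 − 2 = day 2 |
| 5 | (5 − 3) × 24 = 48 h | 1.0 | 5 − 2 = day 3 |
| 6 | (6 − 3) × 24 = 72 h | 1.5 | 6 − 2 = day 4 |

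Holding 48 h for a CT on day 4 or 6 would mean giving the markers on day 2 or 4, which the protocol does not allow for.

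**3. Sensitivity to how days are counted.** Section 9.1.5 words the CT as following five days of treatment. Assume instead that day 3 starts 48 h after treatment start and the CT is at 120 h plus or minus 24 h. The intervals are then 96 − 48 = 48 h, 120 − 48 = 72 h and 144 − 48 = 96 h. The spread is again 48 h, but the centre moves to 72 h. Clock time adds a little: assuming a capsule at 08:00 and a CT between 08:00 and 16:00, the study-day range becomes 24 h to 72 + 8 = 80 h.

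**4. SAP Table 1.** The protocol schedules CTs at baseline and at day 5 plus or minus one day. Neither is day 2-3. That timing does fit the other outcome in the row, the PEG test, which Protocol 7.4.2 runs from 48 to 72 hours after randomization. The next row of Table 1 dates the CT-based complications to day 5.

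**5. Size of the effect on the outcome.** This cannot be calculated. The documents give neither the share of CTs expected on day 4 or 6 nor the rule that converts marker location to a transit time.

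**The case against.** The best defence is that the planned schedule is coherent. Day 3 to day 5 is 48 hours, Section 7.5.1 refers to the planned CT, and the SAP already anchors the capsule to the scan, so a site following the SAP would hold the interval constant. That stands for a CT on day 5. It does not settle what a site following the protocol should do when the CT moves.

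Three stronger readings are tempting, and the documents do not support them.

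- *Transit would be misread by up to half in either direction.* The ratios 0.5 and 1.5 describe elapsed time at the edges of a tolerance window. They are not observed intervals or errors in transit. They would become errors only if the reader assumed 48 hours regardless, and the reading rule is not given.
- *The comparison is biased because patients on active drug go home earlier and are scanned as outpatients.* SAP Section 2.5 does expect shorter admissions on methylnaltrexone, but outpatient CTs share the inpatient window and no passage suggests that they fall earlier or later. Protocol Section 9.3 analyses secondary endpoints per protocol, and the SAP set requires more than 75% of study drug. If that means 75% of five days, the threshold is 0.75 × 120 = 90 hours, which removes many early discharges. The limit is partial: the SAP does not explicitly assign an analysis set to exploratory outcomes, and completers still have the one-day tolerance.
- *Transit would be read before the CT takes place.* The Table 1 entry looks like a timing for the PEG test applied to a merged row.

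**Conclusion.** The conflict is real and minor. The passages agree for a day 5 CT. Counting by study day, the protocol permits about 24 to 72 hours between markers and CT, against the SAP's 48 hours, and the planned test ignores the difference. SAP Table 1 needs correcting in any case.

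The supported consequence is noise, of unknown amount, in one outcome that is secondary in the protocol and exploratory in the SAP. Bias would require CT timing to differ between arms, which is possible but not shown. The primary endpoint and the sample size are not affected. The 24 to 72 hour range rests on counting by study day; under the alternative count in the working it is 48 to 96 hours, and the inconsistency remains.

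**What to change.** 1. Reconcile Protocol Sections 7.5.1 and 9.1.5 with SAP Section 2.3 and Table 1, so that all state one marker-to-CT interval anchored to the CT. The SAP already states 48 hours. Say what happens to the markers when the CT is moved.
2. Use the clock times of the capsule and the CT to calculate each patient's actual interval. The CRF was not among the documents, so check whether both times are already captured.
3. Keep the planned comparison in SAP Section 6.2. Add one sensitivity analysis that either adjusts for the actual interval or is restricted to patients close to 48 hours. Do not scale marker position by time: that assumes markers advance in proportion to time, which nothing in the documents supports.
4. Split the SAP Table 1 row, so that transit is dated to the day 5 (plus or minus one day) CT and permeability keeps its own timing.

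The cost is wording in both documents, two time stamps if they are not already held, one extra analysis, and slightly more coordination when a CT is moved.

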#### 9.1.6. PEG 400/4000 test

Measurement of intestinal permeability and mucosal integrity in patients with AP, will be performed using the oral PEG 400/4000 test (30). In case of intestinal barrier function loss (a leaky gut), the large size molecules (PEG 4000) cross the intestinal barrier, appear into the circulation and becomes detectable in urine after renal excretion. The small size molecules (PEG 400) traverse the intestinal barrier freely, independent of barrier function loss, but is affected in the same way as the large molecules by the pre- and post-mucosal processes including gastric dilution, gastrointestinal motility, bacterial degradation, and renal function. Therefore, the ratio of the urinary concentration of both molecules (PEG 400/4000) more accurately reflect the intestinal permeability and integrity than isolated measurement of a single molecule (31). A PEG solution containing 5 g PEG 400 and 5 g PEG 4000 dissolved in 100 mL water, will be prepared. 48 hours after randomization, the PEG solution is enterally administered via oral intake or a feeding tube and followed by 24-hour urine output collection. Upon collection urine will be homogenized and centrifuged. The supernatant will be desalted by ion-exchange and transferred in aliquots to vials labeled with the protocol number (PAMORA\_2020), subject number, and date of sample collection, which will subsequently be frozen and stored at approximately -80°C or cooler at the respective inclusion sites. Urine samples will be analyzed at a central laboratory to measure the analytes of interest. Excess urine samples will be kept frozen for future research purposes, thereby establishing a biobank. All samples will be destroyed at the latest 15 years after termination of the study. Ethics according to "databeskyttelsesforordningen" and "databeskyttelsesloven" will be ensured in this regard.

## 9.2. Data management

The study will be submitted to the Northern Region of Denmark ("Forskningsanmeldelse Region Nordjylland – Registrering af forskningsprojekter"). Standard operating procedures (SOPs) for data handling and record keeping exists within the research center and these will be followed.

The principal investigator must maintain complete and accurate records to ensure that the execution of the study is fully documented, and the study data can be subsequently verified. These documents should be classified in 2 separate categories: i) researcher Trial Master File and ii) study/participant's clinical source documents (case report form).

Redcap, a secure browser-based software, will be used for filling in the eCRF form for each participant. RedCap meets all regulatory safety requirements and is approved for data collection by the North Danish

Region. Data recording will begin when a participant is included and will occur gradually to the end of the study trial. Any corrections will be made in such a way that information from the original version is still available. The changes endorsed by initials and date. All forms are filled out during (or immediately after) the assessment of a participant and must be legible.

Data will be stored at Aalborg University Hospital, Department of Medical Gastroenterology, for a minimum of 5 years after the study has ended. Relevant information from the participants' medical records will be given to the investigator if needed to assess the in- and exclusion criteria. After five years all data will be anonymized.

The trial master file must contain the protocol/amendments, correspondence with the Danish Health and Medicines Authority, The North Denmark Region Committee on Health Research Ethics and Danish Data Protection Agency, informed consent, staff curriculum vitae, forms, delegation-log, and other appropriate documents/correspondence etc.

The principal investigator at each study site, allows direct access to all source data and documents at monitoring, auditing, and inspection from the Danish Health and Medicines Authority or The Danish Data Protection Agency as well as the GCP-unit at Aalborg and Aarhus University Hospital.

A participant identification list is created for all persons included in the study. This list contains patient number, full name and civil registration number. The list is populated and updated by a study nurse or other competent person and is stored at Department of Gastroenterology, Aalborg University Hospital.

